6.0 ASSESSMENT OF SAFETY

Safety assessments will consist of monitoring and recording DLTs, AEs and SAEs; measurements of protocol-specified hematology, clinical chemistry, urinalysis, and other laboratory variables; measurement of protocol-specified vital signs; and other protocol-specified tests that are deemed critical to the safety evaluation of the study drug(s).

6.1 DEFINITIONS

6.1.1 Adverse Events

An AE is any unfavorable and unintended sign, symptom, or disease temporally associated with the use of an investigational (medicinal) product, regardless of attribution.

This includes the following:

- AEs not previously observed in the subject that emerge during the protocol-specified AE reporting period, including signs or symptoms associated with lung cancer that were not present before the AE reporting period (see [Section 6.2.1](#)).
- Preexisting medical conditions (other than the condition being studied) judged by the investigator to have worsened in severity or frequency or changed in character during the protocol-specified AE reporting period.

Abnormal laboratory values considered clinically significant by the investigator should be reported as AEs.

6.1.2 Serious Adverse Event

The terms “severe” and “serious” are not synonymous. Severity (or intensity) refers to the grade of an AE (see below). “Serious” is a regulatory definition and is based on subject or event outcome or action criteria usually associated with events that pose a threat to a subject’s life or functioning. Seriousness (not severity) serves as the guide

for defining regulatory reporting obligations from the sponsor to applicable regulatory authorities.

An AE should be classified as an SAE if it meets any 1 of the following criteria:

- It results in death (ie, the AE actually causes or leads to death).
- It is life-threatening (ie, the AE, in the view of the investigator, places the subject at immediate risk of death. It does not include an AE that, had it occurred in a more severe form, might have caused death).
- It requires or prolongs inpatient hospitalization.
- It results in persistent or significant disability/incapacity (ie, the AE results in substantial disruption of the subject's ability to conduct normal life functions).
- It results in a congenital anomaly/birth defect in a neonate/infant born to a mother exposed to the investigational product.
- It is considered a significant medical event by the investigator based on medical judgment (eg, may jeopardize the subject or may require medical/surgical intervention to prevent 1 of the outcomes listed above).

6.1.3 Severity

Definitions found in the CTCAE version 4.03 or higher will be used for grading the severity (intensity) of AEs. The CTCAE displays Grades 1 through 5 with unique clinical descriptions of severity for each referenced AE. Should a subject experience any AE not listed in the CTCAE, the following grading system should be used to assess severity:

- Grade 1 (Mild AE) – experiences which are usually transient, requiring no special treatment, and not interfering with the subject's daily activities
- Grade 2 (Moderate AE) – experiences which introduce some level of inconvenience or concern to the subject, and which may interfere with daily activities, but are usually ameliorated by simple therapeutic measures
- Grade 3 (Severe AE) – experiences which are unacceptable or intolerable, significantly interrupt the subject's usual daily activity, and require systemic drug therapy or other treatment
- Grade 4 (Life-threatening or disabling AE) – experiences which cause the subject to be in imminent danger of death
- Grade 5 (Death related to AE) – experiences which result in subject death

6.2 DOCUMENTING AND REPORTING OF ADVERSE AND SERIOUS ADVERSE EVENTS

The investigator is responsible for ensuring that all AEs and SAEs that are observed or reported during the study, as outlined in the prior sections, are recorded on the CRF. All SAEs must be reported on the SAE form or clinical database.

6.2.1 Adverse Event Reporting Period

After the signing of the ICF, all SAEs must be reported. After the first dose of study drug, all AEs, irrespective of seriousness, must be reported.

For acalabrutinib, AE reporting, irrespective of seriousness, ends 30 days after the last dose of study drug(s). For pembrolizumab, all AEs must be reported through 30 days after the last dose of pembrolizumab; any SAEs, or follow-up to a SAE, including death due to any cause other than progression of the cancer under study, must be reported through 90 days after the last dose or 30 days after the last dose of pembrolizumab if the subject initiates a new anticancer therapy within the 90 day posttreatment timeframe.

SAEs considered related to study drug(s) occurring after the end of the AE reporting period (as defined above) must be reported.

If an SAE is present at the last study visit, the SAE should be followed to resolution or until the investigator assesses the subject as stable, or the subject is lost to follow-up or withdraws consent. Resolution/stable means the subject has returned to baseline state of health or the investigator does not expect any further improvement or worsening of the event.

6.2.2 Assessment of Adverse Events

Investigators will assess the occurrence of AEs and SAEs at all subject evaluation timepoints during the study. All AEs and SAEs whether volunteered by the subject, discovered by study personnel during questioning, or detected through physical examination, or other means, that occur to any subject from the time of first dose through 30 days following the cessation of study drug(s), and all SAEs that occur to any subject receiving pembrolizumab from the time of first dose through 90 days following cessation of pembrolizumab, or 30 days following cessation of pembrolizumab if the subject initiates new anticancer therapy (whichever is earlier) will be recorded in the subject's medical record and on the AE CRF.

Disease progression itself is not considered an AE; however, signs and symptoms of disease progression may be recorded as AEs or SAEs.

Each recorded AE or SAE will be described by its diagnostic term, duration (eg, start and end dates), severity, regulatory seriousness criteria, if applicable, suspected relationship to the study drugs (see following guidance), and any actions taken. The causality of AEs to the study drugs will be assessed by means of the question: 'Is there a reasonable

possibility that the event may have been caused by the study drugs?’ per FDA guidance on safety reporting requirements ([FDA Guidance 2012](#)).

See [Appendix 3](#) for more detail on assessing causality.

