3.0 STUDY DESIGN

This clinical trial is a Phase 2, multicenter, open-label, randomized study evaluating pembrolizumab monotherapy and the combination of acalabrutinib and pembrolizumab in subjects who have recurrent or metastatic NSCLC.

Subjects meeting the eligibility criteria for the study will be randomized 1:1 to one of the following arms:

Arm 1: Pembrolizumab 200 mg administered as an IV infusion every 3 weeks (Q3W)

Arm 2: Acalabrutinib 100 mg administered PO BID plus pembrolizumab 200 mg IV Q3W

Acalabrutinib treatment can continue for subjects who are tolerating therapy and not progressing. Pembrolizumab treatment is for 24 months from the date of first dose for subjects who are tolerating therapy and not progressing. Subjects who progress on the combination of pembrolizumab and acalabrutinib will discontinue study treatment while those with progression of disease in the pembrolizumab monotherapy arm will continue on pembrolizumab with the addition of acalabrutinib until a second disease progression or intolerance to therapy. For subjects who cross over to receive combination treatment, acalabrutinib treatment will begin at the next visit at which subjects are scheduled to receive pembrolizumab. The dose of acalabrutinib for these subjects will be determined based on the DLT review of Arm 2. Disease progression will be determined based on irRECIST guidelines ([Appendix 8](#) and detailed in [Section 3.11](#)).

[figure not shown]
Pembrolizumab treatment can end for subjects with confirmed CR if treatment has been administered for at least 24 weeks and 2 doses of pembrolizumab have been administered after confirmation of CR. Treatment on this protocol can continue for a minimum of 12 months after the last subject is randomized.

All subjects will have hematology, chemistry, and urinalysis safety panels performed at screening. Once dosing commences (Day 1), all subjects will be evaluated for safety, including serum chemistry, serum amylase and lipase, and hematology. PD and PK testing will be performed during the first few months of treatment. Radiologic tumor assessments will be completed at baseline and at ~6-week intervals during the trial. Subjects who discontinue study drug for any reason other than disease progression,

death, lost to follow-up, or withdrawal of consent will be followed for tumor assessment until disease progression or initiation of any other anticancer therapies, whichever comes first.

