3.8.2 Supportive Care Guidelines for Pembrolizumab

Subjects should receive appropriate supportive care measures as deemed necessary by the treating investigator. Suggested supportive care measures for the management of adverse events with potential immunologic etiology are outlined below. Where appropriate, these guidelines include the use of oral or intravenous treatment with corticosteroids as well as additional anti-inflammatory agents if symptoms do not improve with administration of corticosteroids. Note that several courses of steroid tapering may be necessary as symptoms may worsen when the steroid dose is decreased. For each disorder, attempts should be made to rule out other causes such as metastatic disease or bacterial or viral infection, which might require additional supportive care. The treatment guidelines are intended to be applied when the investigator determines the events to be related to pembrolizumab.

Note: If after the evaluation the event is determined not to be related, the investigator does not need to follow the treatment guidance (as outlined below). Refer to [Section 3.8.1](#) for dose modification.

It may be necessary to perform conditional procedures such as bronchoscopy, endoscopy, or skin photography as part of evaluation of the event.

- **Pneumonitis:**

- For **Grade 2 events**, treat with systemic corticosteroids. When symptoms improve to Grade 1 or less, steroid taper should be started and continued over no less than 4 weeks.
- For **Grade 3-4 events**, immediately treat with intravenous steroids. Administer additional anti-inflammatory measures, as needed.
- Add prophylactic antibiotics for opportunistic infections in the case of prolonged steroid administration.

- **Diarrhea/Colitis:**

Subjects should be carefully monitored for signs and symptoms of enterocolitis (such as diarrhea, abdominal pain, blood or mucus in stool, with or without fever) and of bowel perforation (such as peritoneal signs and ileus).

- All subjects who experience diarrhea/colitis should be advised to drink liberal quantities of clear fluids. If sufficient oral fluid intake is not feasible, fluid and electrolytes should be substituted via IV infusion. For Grade 2 or higher diarrhea, consider GI consultation and endoscopy to confirm or rule out colitis.
- For **Grade 2 diarrhea/colitis**, administer oral corticosteroids.
- For **Grade 3 or 4 diarrhea/colitis**, treat with intravenous steroids followed by high dose oral steroids.

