5.4 ENDPOINT DATA ANALYSIS

5.4.1 Safety Endpoint

Safety summaries will include summaries in the form of tables and listings. The frequency (number and percentage) of treatment emergent AEs and events of clinical interest will be reported in each treatment group by Medical Dictionary for Regulatory Activities (MedDRA) System Organ Class and Preferred Term. Summaries will also be presented by the severity of the AE (per Common Terminology Criteria for Adverse Events [CTCAE], v4.03 or higher) and by relationship to study drug (eg, either acalabrutinib, pembrolizumab, or both).

Laboratory shift tables containing counts and percentages will be prepared by treatment assignment, laboratory parameter, and time. Summary tables will be prepared for each laboratory parameter. Figures of changes in laboratory parameters over time will be generated.

Results of vital sign assessments and physical exams will be tabulated and summarized.

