Appendix 3. Adverse Event Assessment of Causality

Is there a reasonable possibility that the event may have been caused by study drugs?

No Yes

The descriptions provided below will help guide the principal investigator in making the decision to choose either “yes” or “no”:

No = There is no reasonable possibility that the event may have been caused by study drugs.

The adverse event:

- may be judged to be due to extraneous causes such as disease or environment or toxic factors
- may be judged to be due to the subject's clinical state or other therapy being administered
- is not biologically plausible
- does not reappear or worsen when study drug is re-administered
- does not follow a temporal sequence from administration of study drug

Yes = There is a reasonable possibility that the event may have been caused by study drugs.

The adverse event:

- follows a temporal sequence from administration of study drug
- is a known response to the study drug based on clinical or preclinical data
- could not be explained by the known characteristics of the subject's clinical state, environmental or toxic factors, or other therapy administered to the subject
- disappears or decreases upon cessation or reduction of dose of study drug
- reappears or worsens when study drug is re-administered

Appendix 4. Schedule of Assessments – Treatment Arms 1 and 2

		Treatment Phase (Weeks) ^b										Safety Follow Visit ^c	Follow-up Phase ^d
Study Weeks	Screening ^a	1	2	3	4	5 ^s	6	7	8	≥10 (Q3W)	ET	+30 days after last dose	Q12W
Study Window	-28 days	± 3 days						± 3 days			+ 3 days	+ 7 days	± 10 days
Informed consent	x												
Confirm eligibility	x												
Medical history	x												
PE ^e /Vital signs ^f /Weight	x	x	x	x	x	x		x		x	x	x	
ECOG status	x	x	x	x	x	x		x		x			
ECG ^g	x	x	x		x			x			x	x	
Lab assessments:													
Pregnancy test ^h	x	x ^q			x			x		x	x	x	
Hematology ⁱ	x	x ^q	x	x	x	x		x		x	x	x	
Serum chemistry ^j	x	x ^q	x	x	x	x		x		x	x	x	
Serum lipase/amylase	x	x ^q		x	x		x		x	x	x	x	
Thyroid panel ^k	x	x ^q					x		Week 13 then Q6W		x	x	
Hepatitis serology ^t	x												
HBV PCR ^u	x			x				x	Week 12 then Q4W			Q4W	
HCV PCR ^v	x								Week 13 and 25				
Urinalysis ^l	x												
T/B/NK cell count ^m		x ^q						x ^q		Week 10 then Q3M			
Serum Ig ⁿ		x ^q						x ^q		Week 10 then Q3M			
Pharmacokinetics ^r		x		x				x					
PD/Biomarkers	Tumor sample ^o	x ^q	x ^q	x ^q	x ^q			x ^q		Week 10 and 13 only ^d			
Arm 1	Pembrolizumab 200 mg Q3W		x		x			x		x			

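### One joint causality question cannot feed the by-drug AE summary planned in Section 5.4.1 for events judged related while a subject is on both drugs

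*Protocol*

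**What the plan says.** **Collection.** Section 6.2.2 requires each recorded AE to carry its "suspected relationship to the study drugs (see following guidance". The guidance it points to begins "The causality of AEs to the study drugs will be assessed by means of the question", and that one question is whether there is a reasonable "possibility that the event may have been caused by the study drugs". Appendix 3 puts the same question, "Is there a reasonable possibility that the event may have been caused by study drugs", with one No and one Yes to choose from. Neither place provides for an answer by drug, and no other section of the protocol does.

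**Planned summary.** Section 5.4.1 will present AEs by severity and "by relationship to study drug (eg, either acalabrutinib, pembrolizumab, or both".

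**Who receives both drugs.** Section 3.0 gives Arm 2 "Acalabrutinib 100 mg administered PO BID plus pembrolizumab 200 mg IV Q3W". Arm 1 starts on pembrolizumab alone. After progression its subjects "will continue on pembrolizumab with the addition of acalabrutinib until a second disease progression or intolerance to therapy".

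**Where else attribution by drug is presupposed.** The guidelines in Section 3.8.2 are "intended to be applied when the investigator determines the events to be related to pembrolizumab", and Section 3.8 contemplates holding either drug or both.

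**The concern.** A stated collection rule does not produce the data that a stated summary needs. This is not detail that can wait for the analysis plan, because no analysis rule can split an answer that was never recorded by drug.

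The item matters enough to settle. Characterising the safety profile of the two drugs is the first-listed primary objective (Section 2.1), and relationship to study drug is a named safety parameter (Section 3.1.1). Section 3.10.1 warns that transaminase elevations may be more frequent and more severe with the combination than with either drug alone, so readers of the safety results will look at how investigators attributed such events. Sections 3.8 and 3.8.2 already require the investigator to think drug by drug. The causality assessment as worded does not record the result of that thinking.

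**Working it through.** There is no design figure to reproduce. The check is whether the collected states map onto the planned ones.

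**Inputs.** Section 6.2.2 and Appendix 3: one yes/no answer for the drugs jointly. Section 5.4.1: categories for acalabrutinib, pembrolizumab, or both. Section 3.0: both drugs in Arm 2 and after crossover. Synopsis, Study Design: up to 37 subjects per arm, which agrees with the 6 DLT-review subjects plus up to 31 more in Section 5.1 (6 + 31 = 37).

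**States needed.** Two drugs with yes or no for each give 2 × 2 = 4 states: neither, acalabrutinib only, pembrolizumab only, both.

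**States collected.** One joint answer gives 2.

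| Joint answer | By-drug state on combined exposure |
|---|---|
| No | neither |
| Yes | acalabrutinib only, pembrolizumab only, or both |

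Only one of the four states (neither) is recovered.

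**What a joint Yes leaves open.** Let Y be the number of events answered Yes during combined exposure, made up of a (acalabrutinib only), p (pembrolizumab only) and b (both), so a + p + b = Y. Events related to acalabrutinib number a + b, and events related to pembrolizumab number p + b. The collected data fix Y alone. Each of these two counts can lie anywhere from 0 to Y, subject only to (a + b) + (p + b) = Y + b ≥ Y.

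**Where a joint Yes is already specific.** Arm 1 before crossover has received only pembrolizumab. The first 6 subjects in the combination arm receive acalabrutinib alone on Day 1 of Week 1 and their first pembrolizumab infusion on Day 2 (Sections 3.5.2 and 4.1.18). In those intervals a Yes can refer to only one drug.

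**What does not use the split.** A DLT needs only a judgement that the event is related to study drug (Section 3.7), and the toxicity stopping rule adopts that definition (Section 5.5). AE frequencies by treatment group (Section 5.4.1) need no attribution at all.

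**After the fix.** Two yes/no answers give 2 × 2 = 4 recorded states, one for each state needed.

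**The case against.** Four arguments stand against the point.

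- **The CRF is not shown.** Section 6.2.2 sends AEs to the CRF, and Section 7.4 says completion guidelines come with the database. The form may hold one relationship field per drug, and Section 5.4.1 suggests that the sponsor expects one. This stands as a limit: the consequence follows only if causality is collected as the protocol words it. The inconsistency in the protocol text remains either way.
- **Section 5.4.1 is illustrative.** Its list is introduced as an example and could be read loosely as related to any study drug, which a joint answer would satisfy. That reading is possible, but naming each drug and then both is more naturally a breakdown.
- **Appendix 3 invites reasoning by drug.** Its supporting criteria mostly refer to study drug in the singular, for instance in asking about known reactions or what happens when dosing stops. That is true, and it cuts both ways: the criteria can point to different answers for the two drugs, yet the form offers one answer.
- **Some drug-level information is kept.** Section 6.2.2 records actions taken for each AE, and Section 5.4.3 covers dose reductions and interruptions. This stands, but an action taken is not a causality judgement.

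A reader might infer more: that the relationship table would be empty for every combination subject, that all related events in crossover subjects are lost, or that the safety evaluation of adding acalabrutinib fails. The documents do not support this. A joint No still means neither. Events in crossover subjects before acalabrutinib starts are already specific to pembrolizumab. Related-or-unrelated tabulation remains possible throughout. The effect of adding acalabrutinib is best read from the randomised 1:1 comparison, which needs no attribution.

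**Conclusion.** The point holds within limits. As written, Section 6.2.2 and Appendix 3 cannot supply the by-drug relationship summary in Section 5.4.1 for AEs judged related while a subject is receiving both drugs. The population concerned is up to 37 Arm 2 subjects plus those Arm 1 subjects who cross over, counted only from the start of acalabrutinib. The protocol does not state how many will cross over, so with 37 in Arm 1 the range is 0 to 37. The number of events cannot be given in advance.

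The conclusion assumes that causality is collected as the protocol words it and that Section 5.4.1 intends a breakdown by drug. It concerns one descriptive safety summary. Response rate, sample size and the safety items that do not use the split are untouched. It is worth correcting because it is cheap to do so, and attribution is most reliable when recorded at the time of the event.

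**What to change.** In Section 6.2.2 and Appendix 3, ask the existing question separately for acalabrutinib and for pembrolizumab, and record a yes/no answer to each (not applicable where that drug has not yet been given). Section 5.4.1 then derives neither, acalabrutinib only, pembrolizumab only and both. If the CRF already works this way, change only the protocol wording to match it.

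If the sponsor does not want attribution by drug, the minimum reconciliation is to limit Section 5.4.1 to related to any study drug. That removes the contradiction but gives up the breakdown.

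If events have already been collected on a joint field, a No carries over as No for each drug. A Yes during combined exposure would need a query to the site, or should be shown as related with the drug not specified.

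The cost is one extra field per AE and short edits in two places. No dose or clinical rule changes. The answers remain investigator judgements in an open-label combination and should be reported as secondary to the between-arm comparison.

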6.2.3 Pregnancy

The investigator should report all pregnancies and pregnancies in the partners of subjects within 24 hours using the Pregnancy Report Form. This form should be faxed or emailed to Acerta Pharma Drug Safety. Any pregnancy-associated SAE must be reported to Acerta Pharma, according to the usual timelines and directions for SAE reporting ([Section 6.2.4](#)).

Any uncomplicated pregnancy that occurs with the subject or with the partner of a treated subject during this study will be reported. All pregnancies and partner pregnancies that are identified during or after this study, wherein the estimated date of conception is determined to have occurred from the time of consent to 90 days after the last dose of acalabrutinib, 120 days after the last dose of pembrolizumab, or 30 days after the last dose of either treatment if the subject initiates new anticancer therapy (whichever is earlier) will be reported, followed to conclusion, and the outcome reported, as long as the subject or partner is willing to participate in follow-up.

A pregnancy itself is not regarded as an AE unless there is suspicion that the investigational product under study may have interfered with the effectiveness of a contraceptive medication. Likewise, elective abortions without complications are not considered AEs. Any SAEs associated with pregnancy (eg, congenital abnormalities/birth defects/spontaneous miscarriage or any other serious events) must additionally be reported as such using the SAE report form.

Subjects should be instructed to immediately notify the investigator of any pregnancies. Any female subjects receiving study drug who become pregnant must immediately discontinue study drug. The investigator should counsel the subject, discussing any risks of continuing the pregnancy and any possible effects on the fetus.

Upon completion of the pregnancy, additional information on the mother, pregnancy, and baby will be collected and sent to [contact].

